With the exception of our preliminary work, the question of whether improving sleep reduces drinking and alcohol-related risks has only been tested in older adults.^(27, 28) In older populations, poor sleep is a well-established alcohol relapse risk factor⁽²⁹⁻³²⁾ but sleep interventions have yielded mixed results.^(29, 33) One challenge for treating sleep problems among older adults with AUDs is that chronic, heavy alcohol exposure can have substantial negative effects on sleep that can persist for two or more years following abstinence.⁽³²⁾ Therefore, it may be more effective to target sleep problems earlier during young adulthood before these negative sleep-alcohol cycles become entrenched. Another potential advantage of sleep interventions is that heavy-drinking young adults are open to information to help them sleep better⁽³⁴⁾ and sleep interventions address alcohol use as standard care.⁽³⁵⁾ In our proposed research, we will evaluate whether daily sleep/alcohol self-monitoring + sleep hygiene advice is more effective than sleep hygiene advice alone as well as whether providing personalized feedback based on diaries and sleep/alcohol trackers can lead to further improvements in alcohol outcomes and the mechanisms by which this may occur. The ultimate goal of this research is to examine improved sleep as an effective treatment target for reducing AUD risk in young adults. We will randomly assign participants to 1 of 3 web-based sleep/alcohol self-monitoring + sleep/alcohol data feedback intervention conditions: (1) web-based sleep hygiene advice; (2) web-based sleep hygiene advice + sleep/alcohol diary self-monitoring; or (3) web-based sleep hygiene advice + sleep/alcohol diary self-monitoring + sleep/alcohol data feedback for two weeks of treatment and monitoring followed by 3 follow up visits. We will measure changes in alcohol consumption and sleep quality in order to address the following aims:

Primary Aim: Examine the effect of sleep condition over time on total drinks consumed over Weeks 4-12, controlling for baseline total drinks. The primary alcohol outcome will be change over time in total drinks consumed. Secondary alcohol outcomes will include changes in total drinks per day, drinks per drinking day, alcohol-related consequences, and estimated blood alcohol levels from the alcohol tracker. We hypothesize that participants in the A+SM+F condition will demonstrate the greatest reductions in total drinks of all 3 conditions

HIC # 2000021048

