[name] will apprise fellow investigators and study personnel of all UPIRSOs and adverse events that occur during the conduct of this research project. [name] will hold weekly study meetings with investigators to review study progress, including any adverse events. Investigators who are not present at these meetings will be alerted via email by [name].

The protocol's research monitor(s), e.g., the Yale IRB and NIH will be informed of *any adverse events that meet these 3 criteria: (1) unexpected, (2) related/possibly related to study participation, and (3) places subjects or others at greater risk of harm than previously known/recognized*. These adverse events will be reported within 48 hours of the event becoming known to [name].

13. Statistical Considerations: Describe the statistical analyses that support the study design.

The goal of the Primary Aim is to examine the effect of sleep condition over time on total drinks consumed over Weeks 4-12, controlling for baseline total drinks. For this analyses, we will evaluate changes in scores using a mixed model repeated measures analysis with sleep condition and sex as between-subject factors and time as a within-subject factor. We will also test changes in secondary alcohol outcomes: drinks per day, drinks per drinking day, alcohol-related consequences, and estimated blood alcohol level, controlling for baseline alcohol outcomes, for which we will adjust for multiple comparisons. A mixed model will account for the correlation in alcohol outcomes measured in the same individual and will allow us to use all available data on individuals. The best-fitting variance-covariance structure will be selected using Schwartz-Bayesian Information Criterion (BIC). Time will be considered as a categorical factor but we will also evaluate whether alcohol outcomes change linearly by sleep condition over time. Where appropriate, we will apply transformations (e.g. log) to the dependent measures to comply with model assumptions or we will employ alternative methods (i.e. resampling, nonparametric tests). Expected Results: We hypothesize that participants in the A+SM+F condition will demonstrate the greatest reductions in total drinks of all 3 conditions which will correspond to significant group by time effects with significant between-group differences in change from baseline to end-point.

Statistical Analyses for Secondary Aim

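### The primary outcome has no multiplicity rule, and its only stated criterion, a group-by-time effect, does not test the end-point or average difference between arms

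*Combined protocol and SAP*

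**What the plan says.** Section I, 13 (Statistical Considerations) sets the Primary Aim as to "examine the effect of sleep condition over time on total drinks consumed over Weeks 4-12, controlling for baseline total drinks". The analysis is a mixed model with condition and sex between subjects and time within. On time it says: "Time will be considered as a categorical factor but we will also evaluate whether alcohol outcomes change linearly by sleep condition over time".

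The expected primary result is that "participants in the A+SM+F condition will demonstrate the greatest reductions in total drinks of all 3 conditions", shown by "significant group by time effects with significant between-group differences in change from baseline to end-point". The section names no significance level, lists no pairs and gives no order of testing.

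The only multiplicity statement, "for which we will adjust for multiple comparisons", follows the list of secondary alcohol outcomes and applies to those.

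The Statement of Purpose (Section I, 1) poses two component questions: whether "daily sleep/alcohol self-monitoring + sleep hygiene advice is more effective than sleep hygiene advice alone as well as whether providing personalized feedback" adds further benefit. With the hypothesis that A+SM+F is best of the three, all three pairs (A+SM+F vs A, A+SM+F vs A+SM, A+SM vs A) are in play.

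**The concern.** With three arms, an overall test followed by unadjusted pairwise tests controls the family-wise error, provided the overall test and the pairs concern the same effect. Here they do not. The overall effect named is condition by time, while the pairwise differences are at end-point.

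Two things are at stake. If the benefit is present by Week 4 and holds to Week 12, the interaction will usually be non-significant although the arms really differ. If the arms differ early and then converge, the interaction can be significant while every end-point comparison is a true null tested without adjustment. Either way, the trial's main statement about which component works rests on a test that does not address it.

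**Working it through.** **Inputs.** From the documents: three arms, 2:1:1 allocation (Section I, 4), 140 participants excluding pilots (Section III, 1), hence 70/35/35; follow-up at Weeks 4, 8 and 12. Assumed, because not stated: two-sided 5%, normal outcome, correlation 0.6 between visits, no dropout, sex factor omitted. The plan gives no error rate or power, so there is no figure of its own to reproduce.

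**What each test asks.** Let δ4, δ8, δ12 be the baseline-adjusted difference between two arms at each visit.
- Group-by-time null: δ4 = δ8 = δ12 for every pair (2 × 2 = 4 df).
- End-point null: δ12 = 0.
- Average null: (δ4 + δ8 + δ12)/3 = 0.

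A constant difference of any size satisfies the first null and violates the other two.

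**Sustained difference.** Take A+SM+F 0.6 SD and A+SM 0.3 SD better than A at every visit (SD of the residual after baseline).
- Weighted mean: (70×0.6 + 35×0.3)/140 = 0.375.
- Noncentrality at Week 12: 70×0.225² + 35×0.075² + 35×0.375² = 3.54 + 0.20 + 4.92 = 8.66. The 2-df F test (2 and 137 df) has 74% power; simulation gives 74–75%.
- Average over three visits: variance (1 + 2×0.6)/3 = 0.733, noncentrality 8.66/0.733 = 11.8, power 87%.
- The 4-df interaction is significant in about 5% of simulated trials (5.4–5.5%), which is its false-positive rate.

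**Pairwise error without a binding overall test.** Independent tests would give 1 − 0.95² = 9.75% for two and 1 − 0.95³ = 14.3% for three. Allowing for shared arms at 70/35/35 (1,000,000 draws):
- any of three pairs: 12.1%
- A+SM+F against either other arm: 9.4%
- the two component steps (A+SM vs A, A+SM+F vs A+SM): 8.9%

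**Pairwise error with a significant interaction required.** Table entries are the chance of any false Week 12 pairwise claim. The early differences are for A+SM+F/A+SM against A at Week 4, halved at Week 8 and zero at Week 12.

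| Early difference (SD) | Interaction required | 2-df Week 12 test required |
|---|---|---|
| none at any visit | 1–2% | about 5% |
| 0.3/0.15 | 3–4% | about 5% |
| 0.6/0.3 | 9.0% | about 5% |
| 0.8/0.4 | 11.2% | about 5% |

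The range in the first row reflects how correlation is modelled. Taking 0.6 as the residual correlation gives about 1%. Taking 0.6 as the raw correlation leaves (0.6 − 0.36)/(1 − 0.36) = 0.375 after baseline adjustment and gives about 2%.

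**If baseline is instead a level of time (6 df).** A constant 0.6 SD benefit in A+SM+F alone (raw SD) is then detected in about 97% of trials, against about 5% for the 4-df version. Protection at Week 12 is weaker, however. With a 0.5 SD early effect in A+SM+F that fades, the false-claim rate is 11.5–11.9%, against 8.4–9.4% for the 4-df version.

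**The case against.** The strongest reply is that the plan states no such procedure. The sentence on group-by-time effects is a hypothesis about results. It joins the interaction and the between-group differences without putting one before the other. A reader might infer that the plan formally gates unadjusted pairwise tests on the interaction, or that the trial carries a 9–12% chance of a false primary claim. The documents support neither as a flat statement. The gate is an inference, and the error runs from about 1% to about 12% depending on the reading.

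The fading scenario is also undocumented. In the preliminary study (Section I, 3, Table 1) the between-arm gap in typical-week drinks was 16.34 − 13.63 = 2.71 at Week 5 and 11.15 − 8.56 = 2.59 at three months. The heaviest-week gap grew from 7.23 to 9.30. Taking SE×√21 as the SD (9.58 and 6.60, pooled 8.23), the Week 5 typical-week gap is about 2.71/8.23 = 0.33 SD, well short of 0.6–0.8. Those arms differ from the present ones and had 21 participants each. Moreover, if arms differ early and converge, they do differ on average over Weeks 4–12, so only a Week 12 claim would be false.

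Finally, if success meant A+SM+F beating both other arms, no adjustment would be needed: both tests are significant in about 0.6% of trials under the complete null, and in at most 5% otherwise. The plan does not set that rule, and its Statement of Purpose also asks about A+SM versus A.

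All of this limits the error figure. It leaves standing the missing rule for the primary outcome and, under the covariate reading, the insensitivity to a sustained effect. The preliminary typical-week gap, nearly constant after baseline, illustrates the pattern that the interaction would miss. The 6-df coding would remove that insensitivity, but the plan describes controlling for baseline and does not specify that coding.

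**Conclusion.** The point holds in this form. The primary outcome has no multiplicity rule, and the one criterion offered does not test the difference that the primary claim is about. The loss of sensitivity is the firmer half: about 5% against about 75% for a sustained 0.6/0.3 SD effect, given baseline as a covariate, 70/35/35, correlation 0.6 and two-sided 5%.

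The error half is conditional. It is about 12% for any of three pairs (about 9% for two) if the interaction does not bind. If it binds, the error is 1–2% when the arms never differ and 3–4% after a 0.3 SD early effect that fades. Only a 0.6–0.8 SD early effect that vanishes by Week 12 brings it to 9–11%. The plan should be amended, but nothing here shows that the trial's error rate is 12%.

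**What to change.** State two-sided 5%. Name one baseline-adjusted quantity for the primary outcome: the average over Weeks 4–12, which matches the stated aim, or the Week 12 difference. Make the primary test the 2-df condition effect on that quantity. Only if it is significant, test the three pairwise contrasts on the same quantity at 5% each. With three arms this is a closed procedure and controls the family-wise error. Report group-by-time as a description of the time course.

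The cost is wording in Section I, 13, with no change to design, sample size or data collection. The downside is that no pairwise claim can be made unless the overall test is significant. Bonferroni over the three pairs would avoid that and gives a family-wise error of 4.4%, but it tests each pair at 1.67%.

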which will correspond to significant group by time effects with significant between-group differences in change from baseline to end-point.

Secondary Aim 1: Examine the effect of sleep condition on sleep quality ratings over time, controlling for baseline ratings. The primary sleep outcome will be change in sleep quality ratings (i.e., the perception of how well one has slept) over time. Secondary sleep outcomes will include changes in ratings of sleep-related impairment and sleep tracker quantitative characteristics (i.e., duration, efficiency, % awake, bed/wake times). We hypothesize that participants in the A+SM+F condition will demonstrate the greatest improvements in sleep quality of all 3 conditions which will correspond to significant group by time effects with significant between-group differences in change from baseline to end-point.

Secondary Aim 2: Use descriptive statistics to summarize participants' acceptability ratings of web-based sleep hygiene advice, sleep/alcohol diary self-monitoring, sleep/alcohol tracker use, and personalized sleep/alcohol data feedback. We anticipate that the A+SM+F condition will yield the highest acceptability ratings of all 3 conditions. A review of participants' reactions to personalized sleep feedback will provide insight into what types of feedback and tailored health tips are feasible and useful for heavy-drinking young adults.

Exploratory Aim 1: Evaluate improvements in sleep quality, self-control (i.e., Stop Signal Task performance), working memory, and behavioral processes over time as mechanisms of sleep condition effects on total drinks. We will calculate individual slope change estimates for sleep quality and self-control and then evaluate these slope estimates as potential mechanisms using a SAS macro outlined by Valeri and VanderWeele.⁽⁶⁹⁾ This method allows for independent variable X mediator interactions and is suitable for count outcomes (i.e., total drinks). Given the smaller sample size for this exploratory research, we will then evaluate correlations between sleep quality and self-control slope estimates rather than use structural equation modeling to model potential complex pathways among sleep condition, sleep quality, self-control, and drinking.

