
Theme 2. Heavy-drinking young adults find sleep interventions appealing, are interested in personalized information about sleep and alcohol interactions, and prefer personalized sleep feedback along with tailored advice.

[name] and the research team conducted a qualitative study with heavy-drinking college students (N=24) to assess their perceptions of sleep and sleep-alcohol interactions and their intervention preferences.⁽³⁴⁾ The following common themes emerged from these interviews: strong interest in sleep treatment and interventions that focused on the interaction between sleep and alcohol use, less enthusiasm for alcohol-related intervention content alone unless it had a sufficient rationale for sleep, and strong preference for intervention strategies that included personalized, tailored health feedback and health advice tailored to this data. These findings support a follow-up study to develop and test a personalized sleep/alcohol data feedback plus tailored advice intervention in heavy-drinking young adults.

Table 1. Estimated means (SE) of alcohol consumption, alcohol-related consequences, and subjective sleep-related characteristics by treatment condition and time

M (SE)	CIAN (n=21)				HB (n=21)			
	Intake	Wk 5	3Mo F/U	Effect Size	Intake	Wk 5	3Mo F/U	Effect Size
Drinks Typical Week	17.95 (2.07)	16.34 (2.09)	11.15 (2.15)	d=.58	18.16 (2.51)	13.63 (1.44)	8.56 (1.72)	d=.65
Drinks Heaviest Week	27.50 (4.41)	25.24 (4.97)	20.40 (4.14)	d=.14	24.96 (2.80)	18.01 (1.91)	11.10 (2.17)	d=.47
Alcohol Consequences	15.83 (1.05)	11.02 (1.16)	8.75 (1.07)	d=1.28	17.05 (.83)	9.48 (.59)	7.72 (.52)	d=2.20
Poor Sleep Quality	11.93 (.46)	10.85 (.44)	8.59 (.58)	d=1.29	11.65 (.46)	10.13 (.43)	7.85 (.42)	d=1.66
Sleep-related Impairment	60.52 (1.67)	56.45 (1.31)	51.29 (1.83)	d=1.11	65.41 (1.40)	55.02 (1.89)	50.14 (1.92)	d=2.18

Theme 3. Daily sleep self-monitoring and sleep tracker use are feasible among heavy-drinking young adults.
Mobile technology to monitor blood alcohol levels is acceptable to young adults.

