In our preliminary study of a mobile sleep intervention for heavy-drinking young adults (N=42), all participants demonstrated adequate adherence to sleep-monitoring activities. Adherence was defined as wearing the sleep tracker 75% of the time and completing 75% of the daily sleep diaries (i.e., 5 days). Adequate adherence during baseline sleep monitoring was a requirement for randomization. Only 1 out of 43 individuals was excluded prior to randomization for not adhering during this baseline period. Of those randomized (N=42), all demonstrated adequate adherence. In our qualitative study to inform initial intervention development, young adults expressed interest in emerging mobile technologies that provide an objective assessment of alcohol consumption.⁽³⁴⁾

4. **Research Plan:** Summarize the study design and research procedures using non-technical language that can be readily understood by someone outside the discipline. **Be sure to distinguish between standard of care vs. research procedures when applicable, and include any flowcharts of visits specifying their individual times and lengths.** Describe the setting in which the research will take place.

We will be conducting a study that will examine improved sleep as an effective treatment target for reducing AUD risk in young adults.

Screening, Intake, and Randomization (Week 0): Participants who meet internet screening eligibility criteria will attend an in-person intake at one of our study sites (the SATU clinic of the Connecticut Mental Health Center (CMHC) located at [name], the main offices of the CMHC located at [name], or the Yale School of Nursing Biobehavioral Lab located at [name]) to learn

HIC # 2000021048

about the study, provide informed, voluntary consent, be further evaluated for eligibility, and complete baseline assessments. If found eligible, participants will be randomly assigned (stratified by gender) to 1 of 3 treatment conditions: Treatment Condition 1: Participants receive only web-based sleep hygiene advice (A); Treatment Condition 2: Participants receive web-based sleep hygiene advice + sleep/alcohol diary self-monitoring (A+SM); Treatment Condition 3: Participants receive web-based sleep hygiene advice + sleep/alcohol diary self-monitoring + sleep/alcohol data feedback (A+SM+F).

[REDACTED]	[REDACTED]	[REDACTED]	[REDACTED]	[REDACTED]
[REDACTED]	[REDACTED]	[REDACTED]	[REDACTED]	[REDACTED]

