[REDACTED] the end of the first seven-day monitoring period, the research assistant will pick up the Actiwatch Spectrum Plus sleep tracker and a AMS Sensor blood-alcohol tracker from the participant. Upon receipt of the sleep trackers, we will download participants' scored sleep and alcohol use data from the prior week to include in the web-based sleep hygiene program and tailor the take-home health tips handouts that participants will receive the next day at each in-person visit. The next day the participant will return for an in-person visit and will receive empirically-supported brief sleep hygiene advice via the web-based program from our prior study. [REDACTED]

Follow-Up Phase: (Weeks 4, 8, 12): Participants will attend a 1 follow-up visit at each of these time points for a total of 3 follow-up visits: Weeks 4, 8, and 12 after starting treatment. At these visits, participants will complete a number of questionnaires that will ask about and assess sleep, mood, health behaviors, alcohol use, psychological characteristics, and will complete a computer task (See Table 3 Variables/Measures below). Participants will also be asked about their use of the tailored health tips based on their sleep data and whether any of the sleep tips were helpful.

Figure 1: Study Flow Chart

[figure not shown]

Table 4: Variables/Measures

Variables	Assessments	Intake	Diary Self-Monitoring	Alcohol/Sleep Trackers	Weeks 1, 2, 4, 8, 12
Eligibility/ Lab/ Medical	Demographics	X			
	DSM-V Diagnoses	X			
	Urine Drug Screen	X			

	Breath Alcohol	X			X
	AUDIT	X			
	Endorse Sleep Concerns	X			
	Height and weight	X			
	Physical Fitness Survey	X			
Alcohol Outcomes	Timeline Followback	X			X
	Alcohol-Related Consequences	X			4, 8, 12
	AMS Tracker Blood Alcohol Level			X	
	Skyn Tracker Blood Alcohol Level			X	
	Drinking Self-Monitoring Log		X		
Sleep Outcomes	PROMIS™ Sleep-related Impairment	X			4, 8, 12
	PROMIS™ Sleep Disturbance	X			4, 8, 12
	Pittsburgh Sleep Diary		X		
	Psychomotor Vigilance		X		
	Positive and Negative Affect Scales	X			4, 8, 12
	Munich Chronotype and Horne-Ostberg Morningness/Eveningness	X			
	Actiwatch: sleep onset/offset; total sleep time; sleep efficiency; % awake			X	
Self-Control	Stop Signal Task	X			4
Working Memory	N-Back Task	X			4
Behavioral Mechanisms	Behavioral Intentions Questionnaire (2 items)	X			
	Global Attitudes Scale	X			
	Subjective Norms Questionnaire	X			
	Drinking Refusal Self-Efficacy Questionnaire	X			4, 8, 12

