*To evaluate potential sleep intervention mechanisms, we will assess several Theory of Planned Behavior (TPB) constructs based on a prior TPB growth model of risky drinking in young adults.^[75] Two internally consistent items from the **Behavioral Intentions Questionnaire** will assess intentions to engage in risky-drinking.^[84] Reliable and valid adapted versions of the **Global Attitudes Scale**^[71, 75, 86] and **Subjective Norms Questionnaire**^[71, 74] will assess participants’ overall opinions about heavy alcohol consumption, perceptions of how others view their drinking, and their perceptions of typical drinking among their peers. A reliable and valid adapted version of the **Drinking Refusal Self-Efficacy Questionnaire**^[71, 75, 90] and additional items suggested by Ajzen will assess participants’ perceptions of being able to control/resist heavy drinking.*

Intervention Component Feasibility and Acceptability:

We will evaluate participant use metrics to determine intervention component feasibility (i.e., diary and tracker adherence, use of health tips during treatment and follow-up). At Week 2, all participants will complete an end of treatment evaluation form. We will also interview participants in A+SM+F to evaluate their reactions to and preferences for sleep/alcohol data monitoring and feedback.

5. Genetic Testing N/A

A. Describe

- i. the types of future research to be conducted using the materials, specifying if immortalization of cell lines, whole exome or genome sequencing, genome wide association studies, or animal studies are planned *Write here* the plan for the collection of material or the conditions under which material will be received *Write here*
- ii. the types of information about the donor/individual contributors that will be entered into a database *Write here*
- iii. the methods to uphold confidentiality *Write here*

B. What are the conditions or procedures for sharing of materials and/or distributing for future research projects? *Write here*

C. Is widespread sharing of materials planned? *Write here*

D. When and under what conditions will materials be stripped of all identifiers? *Write here*

E. Can donor-subjects withdraw their materials at any time, and/or withdraw the identifiers that connect them to their materials? *Write here*

F. How will requests to withdraw materials be handled (e.g., material no longer identified: that is, anonymized) or material destroyed)? *Write here*

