The goal of the Secondary Aim 1 is to examine the effect of sleep condition on sleep quality ratings over time, controlling for baseline ratings. We will use mixed model repeated measures analysis as described above. We will also test changes in secondary sleep outcomes: ratings of sleep-related impairment and sleep quantitative outcomes (i.e., duration, efficiency, % awake, bed/wake times), controlling for baseline responses. Expected Results: We hypothesize that participants in the A+SM+F condition will demonstrate the greatest improvements in sleep quality of all 3 conditions which will correspond to significant group by time effects with significant between-group differences in change from baseline to end-point.

For Secondary Aim 2, we will use descriptive statistics to summarize participants' acceptability ratings of web-based sleep hygiene advice, sleep/alcohol diary self-monitoring, sleep/alcohol tracker use, and personalized sleep/alcohol data feedback. We anticipate that the A+SM+F condition will yield the highest acceptability ratings of all 3 conditions. A review of participants' reactions to personalized sleep feedback will provide insight into what types of feedback and tailored health tips are feasible and useful for heavy-drinking young adults.

For Exploratory Aim 1, we will evaluate improvements in sleep quality over time and self-control (i.e., Stop Signal Task performance), working memory, and behavioral processes as mechanisms of sleep condition effects on total drinks at Month 3. We will calculate individual slope change estimates for sleep quality and then evaluate these slope estimates as potential mechanisms using a SAS macro outlined by Valeri and VanderWeele. (69) This method allows for independent variable X mediator interactions and is suitable for count outcomes (i.e., total drinks). Given the smaller sample size for this exploratory research, we will then evaluate correlations between

HIC # 2000021048

sleep quality slope estimates and self-control rather than use structural equation modeling to model potential complex pathways among sleep condition, sleep quality, self-control, and drinking.

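### Exploratory Aim 1: as Table 4 reads, three of the four behavioural-mechanism scales are measured only before randomisation, so they could not be tested as mediators

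*Combined protocol and SAP*

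**What the plan says.** Exploratory Aim 1 in Section I, 1 (Statement of Purpose) sets out to evaluate, among other mechanisms, "working memory, and behavioral processes over time as mechanisms of sleep condition effects on total drinks". Section I, 13 (Statistical Considerations) repeats the aim with the outcome dated: "behavioral processes as mechanisms of sleep condition effects on total drinks at Month 3. We will calculate individual slope change estimates for sleep quality".

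The Behavioral Mechanisms text in Section I, 4 (Research Plan) gives the purpose of the scales: "To evaluate potential sleep intervention mechanisms, we will assess several Theory of Planned Behavior (TPB) constructs based on a prior TPB growth model". It describes four instruments (intentions, attitudes, norms, refusal self-efficacy) and gives visit dates for none of them.

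Table 4 is the only place where these four scales are scheduled. The row beginning "Behavioral Intentions Questionnaire (2 items" and the rows for Global Attitudes and Subjective Norms are marked at intake, and their follow-up cells are empty. The row "Drinking Refusal Self-Efficacy Questionnaire" is marked at intake and at Weeks 4, 8 and 12.

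The Screening, Intake, and Randomization paragraph fixes the order of events at intake. Participants "complete baseline assessments. If found eligible, participants will be randomly assigned (stratified by gender) to 1 of 3 treatment conditions".

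**The concern.** To mediate the effect of a randomised condition, a variable must be able to respond to that condition. It therefore has to be measured at least once after randomisation. The aim also speaks of change over time, and the scales are modelled on a growth model; both imply repeated scores. Three blank follow-up cells contradict this.

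The missing constructs are not peripheral. The Background (Section I, 3) explains the expected benefit of self-monitoring and feedback partly through beliefs about behaviour change and intentions to change. Intentions and attitudes are two of the three scales without follow-up. If the schedule is applied as read, most of the behavioural model could not be examined. Scores not collected at a visit cannot be recovered once that visit has passed.

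**Working it through.** The plan gives no figure on this point, so there is none to reproduce. The check compares the schedule with the aim, then works out what an intake-only score can show and which visit could supply the missing measurement.

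**Step 1: count the measurements (Table 4, Behavioral Mechanisms block).**

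| Scale | Intake | Follow-up cell | Values after randomisation |
|---|---|---|---|
| Behavioral Intentions | X | blank | 0 |
| Global Attitudes | X | blank | 0 |
| Subjective Norms | X | blank | 0 |
| Drinking Refusal Self-Efficacy | X | 4, 8, 12 | 3 |

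As read, 1 of 4 scales has post-randomisation values and 3 of 4 have none.

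**Step 2: what an intake-only score can show.** Let M0 be the intake score. Randomisation follows intake, so the distribution of M0 is the same in every arm in expectation. The condition-to-mediator path is a = E[M0 | A+SM+F] − E[M0 | A] = 0. An indirect effect compares outcomes under the mediator distributions of two conditions. Those distributions are identical here, so the indirect effect is zero whatever the relation of M0 to drinking. Allowing a condition-by-mediator interaction, as the planned macro does, changes nothing.

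The estimated path in one trial will differ from zero by chance. Assume 140 participants split exactly 2:1:1 (70, 35, 35), no dropout, and a score with SD 1. The standard deviation of the A+SM+F minus A difference is then √(1/70 + 1/35) = √0.0429 = 0.21 SD. A simulation under the same assumptions gave a mean difference of −0.001 SD with a spread of 0.20 SD. Any apparent mediation through these three scores would be baseline imbalance.

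**Step 3: does a blank mean not assessed?** Other Table 4 rows can be compared with dates in the measures text.
- The chronotype row is blank at follow-up, and the text says that measure is given at intake.
- The two PROMIS rows and the affect row each carry 4, 8, 12, and the text agrees.
- Stop Signal and N-Back each carry 4, and the text agrees.
- Adjacent rows with the same schedule repeat the entry instead of sharing one cell.
- Merged category labels stand on the first row of their block. The single 4, 8, 12 in this block stands on the last row.

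These comparisons favour reading the blanks as intake only. They do not prove it.

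**Step 4: which follow-up visit precedes the outcome?** Take total drinks at Month 3 as the 30-day Timeline Followback summary at Week 12, with visits on schedule and all weeks counted from one start.
- Window: day 12 × 7 = 84, back to day 84 − 30 = 54.
- Week 4: day 28, which is 54 − 28 = 26 days before the window opens.
- Week 8: day 56, which is 56 − 54 = 2 days inside the window.
- Week 12: day 84, at the end of the window.

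Of the three follow-up visits, only Week 4 precedes the window.

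**The case against.** The strongest reply is that the point rests on three empty cells in a table read from PDF by a program. The table breaks across pages, the study flow chart is not shown, and another table is redacted. The follow-up column is also filled loosely: Timeline Followback has a plain X under a heading of Weeks 1, 2, 4, 8 and 12, while the text derives its summary variables at intake and Weeks 4, 8 and 12. The prose can be read as favouring an omission. It speaks of change over time, cites a growth model, and says that at follow-up visits "participants will complete a number of questionnaires that will ask about and assess sleep, mood, health behaviors, alcohol use, psychological characteristics". Nowhere does it say that the three scales are intake only.

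Part of this stands. A lost or merged cell cannot be excluded, and the documents do not show that the investigators chose to measure these scales once. A reader might infer such a decision, but the prose leans the other way. The reply does not dispose of the point, however. The follow-up sentence names none of the three scales, the measures text gives no visits for them, and the rows that can be checked show a blank meaning intake only. Even if the blanks are a slip, the schedule that staff would follow does not serve the stated aim and needs correcting.

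A reader might also infer that the sleep-quality slope is faulty because a Week 12 rating could enter it and fall within the Month 3 drinking window. The documents do not support calling that an error. They do not say which visits enter the slope, and leaving out later ratings is a design choice that can cost precision.

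**Conclusion.** The point holds conditionally. If Table 4 is applied as it reads, 3 of the 4 behavioural scales have no post-randomisation value and cannot be evaluated as mediators. No analysis method can repair that afterwards. The conclusion rests on two things: that the blank cells mean not assessed, which is likely but unconfirmed, and that intake scores are taken before assignment, as the protocol describes.

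A reader might infer that Exploratory Aim 1 as a whole cannot be carried out. The documents do not support this. Refusal self-efficacy is scheduled three times after randomisation, Stop Signal and N-Back at Week 4, and PROMIS Sleep Disturbance at Weeks 4, 8 and 12. The primary and secondary analyses do not use the three scales. Priority is low. The documents give no enrolment status, so it cannot be said whether the missing scores could still be collected.

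**What to change.** Reconcile Table 4 with Exploratory Aim 1 (Section I, 1 and 13) and with the Behavioral Mechanisms text in Section I, 4.

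1. **If the blanks are an omission or a reading artefact:** confirm or correct the table, and state the visits for all four scales in the measures text. This is an editorial change.
2. **If the blanks are intended,** choose one of two routes.
   - Add Behavioral Intentions, Global Attitudes and Subjective Norms at the existing Week 4 visit, beside refusal self-efficacy and the two computer tasks. The cost is slightly more questionnaire time; Intentions has 2 items, and the length of the other two is not given. For anyone already past Week 4, intake scores can serve only as moderators or covariates.
   - Leave the schedule alone, limit the behavioural-mediator claim to refusal self-efficacy, and name the three intake-only scores as moderators or covariates. This adds no participant burden but gives up testing intentions, attitudes and norms as mechanisms.
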